Review of safety, PK and pharmacodynamic profiles may inform decisions to add cohorts with alternative dose levels or dose regimens (eg, different dosing frequency, higher dose levels) in order to reach an optimal target exposure.

All dose escalation decisions will be based on the assessment of dose-limiting toxicities (DLTs) and overall safety and tolerability. Dose escalation decisions will be made after the last patient enrolled in each cohort has completed the first treatment cycle (ie, 21 days). Dose escalation decisions will be agreed upon by the Cohort Review Committee (CRC), consisting of at least the Sponsor's Medical Monitor and defined quorum of Study Investigators.

Dose-Limiting Toxicity Definitions:

DLTs during Phase 1a Dose Escalation are defined as any of the following events regardless of attribution (except for those events clearly due to the underlying disease or extraneous causes):

- Any Grade 3 or higher non-hematologic toxicity (except Grade 3 nausea, vomiting and diarrhea) occurring within the 21 days of treatment
- Grade 3 nausea, vomiting, diarrhea lasting > 72 hours, despite optimal supportive care, occurring within first 21 days of treatment
- Febrile neutropenia and/or documented infection with absolute neutrophil count (ANC) < 1.0×10^9 per L, Grade 4 neutropenia lasting for more than 7 days, Grade 4 thrombocytopenia (< 25.0×10^9 per L), or Grade 3 thrombocytopenia (< $50.0-25.0 \times 10^9$ per L) accompanied by bleeding within first 21 days of treatment
- Aspartate aminotransferase/ alanine transaminase (AST/ALT) > $3 \times$ upper limit of normal (ULN) and concurrent total bilirubin > $2 \times$ ULN not related to liver involvement with cancer
- Any Grade 4 laboratory value regardless of clinical sequelae
- Other Grade 3 laboratory values that are not of clinical significance according to Investigator and Sponsor agreement that do not resolve within 72 hours

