4.1.2.2 Definition of a Dose-Limiting Toxicity

4.1.2.2.1 FPA150 Monotherapy

DLTs during Phase 1a Dose Escalation are defined as any of the following events regardless of attribution (except for those events clearly due to the underlying disease or extraneous causes):

- Any Grade 3 or higher non-hematologic toxicity (except Grade 3 nausea, vomiting and diarrhea) occurring with the first 21 days of treatment
- Grade 3 nausea, vomiting, diarrhea lasting > 72 hours, despite optimal supportive care, occurring within first 21 days of treatment
- Febrile neutropenia and/or documented infection with absolute neutrophil count (ANC) < 1.0×10^9 per L, Grade 4 neutropenia lasting more than 7 days, Grade 4 thrombocytopenia (< 25.0×10^9 per L), or Grade 3 thrombocytopenia (< $50.0-25.0 \times 10^9$ per L) accompanied by bleeding within first 21 days of treatment
- Aspartate aminotransferase/alanine transaminase (AST/ALT) > 3 × upper limit of normal (ULN) and concurrent total bilirubin > 2 × ULN not related to liver involvement with cancer
- Other Grade 3 laboratory values that are not of clinical significance according to Investigator and Sponsor agreement that do not resolve within 72 hours
- Any Grade 4 laboratory value regardless of clinical sequelae

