6.4.4 Dose Modification Criteria for FPA150

Dose reductions for FPA150 may be permitted for patients on treatment beyond the DLT Period and can be assessed using local laboratories. If a patient requires a dose reduction of FPA150 during the DLT period, they will be considered to have a DLT and be permanently discontinued from FPA150. Dose reductions for FPA150-related AEs should follow the guidelines outlined in [Table 10](#). The treating physician may choose to interrupt or discontinue FPA150 at any time outside of these guidelines if they believe it is necessary to ensure patient safety. It is recommended that the treating physician discuss the proposed dosing modification with the FivePrime medical monitor prior to making the change. Patients may resume FPA150 if the event returns to baseline or \leq Grade 1 in accordance with the guidelines outlined in [Table 10](#). Any variations from these guidelines must be discussed with the FivePrime Medical Monitor prior to dosing and must take into consideration the overall benefit and risks for the patient of continued participation in the study.

Table 10: Dose Modification Guidelines for FPA150 (Non-infusion Toxicity)

FPA150-related Toxicity Grade	Dose Schedule	New FPA150 Dose
Grade 1 or 2	No delay or missed dose required	100% of dose
Grade 3 (first occurrence)	Delay or miss dose until recovery to baseline or Grade 1	If recovery to baseline or Grade 1 within 28 days, may resume at 100% of starting dose or 1 dose lower ^a
Grade 3 (second occurrence)	Delay or miss dose until recovery to baseline or Grade 1	If recovery to baseline or Grade 1 within 28 days, may resume at 1 level lower ^a than previous dose or discontinue
Grade 3 (third occurrence) Grade 3 which does not recover to baseline or Grade 1 within 28 days Any Grade 4	Permanently Discontinue	N/A

^a Eg, 1 dose level lower for patients treated at 20 mg/kg is 10 mg/kg; 1 dose level lower for patients treated at 10 mg/kg is 3 mg/kg; 1 dose level lower for patients treated at 3 mg/kg is 1 mg/kg.

There is a \pm 3-day window for the first 3 scheduled FPA150 dosing visits. The first dose of each cycle is considered Day 1 of each cycle. Cycles will repeat every 21 days unless there is a treatment delay. Inpatient dose escalation will not be permitted above 1mg/kg except as detailed in [Section 6.4.2](#). Any patient whose dose of FPA150 is decreased cannot be subsequently increased.

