6.4.5 Dose Modification Criteria (Pembrolizumab) including Immune Related AEs

Any dose modifications for pembrolizumab-related toxicity in patients enrolled on the Phase 1a Safety Lead-in will be considered a DLT and the patient will need to be replaced.

Dose modifications for pembrolizumab in the Phase 1b dose expansion will be allowed in accordance with the Keytruda® USPI. Dose reductions for pembrolizumab are not permitted. AEs associated with pembrolizumab exposure may represent an immunologic etiology. These irAEs may occur shortly after the first dose or several months after the last dose of pembrolizumab treatment and may affect more than one body system simultaneously. irAEs may be managed with interruptions of pembrolizumab, administration of corticosteroids and/or other supportive care. Dose modification and toxicity management for irAEs associated with pembrolizumab should be done in accordance with the guidelines provided in the Keytruda® USPI.

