APPENDIX 4:	EASTERN COOPERATIVE ONCOLOGY GROUP PERFORMANCE STATUS.....	120
APPENDIX 5:	CLINICAL LABORATORY TESTS.....	121
APPENDIX 6:	NEW YORK HEART ASSOCIATION CLASSIFICATION.....	123
APPENDIX 7:	PROTOCOL AMENDMENT HISTORY	124

APPENDIX 1: SCHEDULE OF ASSESSMENTS**Table 12: Schedule of Assessments: Phase 1a and Phase 1b (Monotherapy and Combination Cohorts)**

Procedure ^{a,b}	Pre-Screening	Screening	Cycle 1		Cycle 2	Subsequent Cycles	End of Treatment Follow-up Period		LTFU Period ^p
		Day -28 to Day 0	Day 1 ^q ± 3 days	Day 8 ± 3 days	Day 1 ± 3 days	Day 1 ± 3 days	28 (±7) days post-last dose	100 (±7) days post-last dose	
Informed Consent	x ⁱ	x							
Review / Confirm Eligibility Criteria		x	x						
Medical History / Demographics		x	x						
Physical Examination ^c		x	x	x	x	x	x	x	
Height and Weight ^{c,d}		x	x		x	x	x	x	
Vital Signs ^e		x	x	x	x	x	x	x	
12-Lead ECG ^f		x					x	x	
ECOG Performance Status ^g		x	x		x	x	x	x	
Fresh Biopsy ^h		x				x			
Archival Tissue for IHC Testing for B7-H4 and Exploratory Biomarker Analyses ⁱ	x	x							
Clinical Safety Laboratory Tests ^j		x	x	x	x	x	x	x	
Hepatitis B (HBsAg and HBcAb), and Hepatitis C (HCV RNA)		x							
CT/MRI Tumor Assessment ^k		x				x	x		x
Tumor Markers ^l	Refer to Appendix 2 for specific days and times								
Pregnancy Test ^m		x	x			x	x		
Sampling for PK, ADA, and Pharmacodynamics ⁿ	Refer to Appendix 2 for specific days and times								

Procedure ^{a,b}	Pre-Screening	Screening	Cycle 1		Cycle 2	Subsequent Cycles	End of Treatment Follow-up Period		LTFU Period ^p
		Day -28 to Day 0	Day 1 ^q ± 3 days	Day 8 ± 3 days	Day 1 ± 3 days	Day 1 ± 3 days	28 (±7) days post-last dose	100 (±7) days post-last dose	
Study Drug(s) ^o			x		x	x			
Adverse Events ^s			x	x	x	x	x		
Prior/Concomitant Medications			x	x	x	x	x		
Thyroid Function Testing ^f			x			x			
Long-Term Follow-up Contact ^p									x

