Abbreviations (for the Schedule of Assessments and Footnotes): ADA = anti-drug antibody; AE = adverse events; ALT = alanine transaminase; AST = aspartate transaminase; B7-H4 = transmembrane protein of the B7 family also known as B7S1, B7x, or VTCN1; CK = creatinine kinase; CT = computerized tomography; DOR = duration of response; ECG = electrocardiogram; ECOG = Eastern Cooperative Oncology Group; EOT = End of Treatment; HBsAg = hepatitis B surface antigen; HCV = hepatitis C antibody; IV = intravenous; LTFU = long-term follow-up; MRI = magnetic resonance imaging; PK = pharmacokinetics; Q3W = once every 3 weeks; Q12W = once every 12 weeks; RECIST v1.1 = Response Evaluation Criteria in Solid Tumors version 1.1.

Additional guidance for sampling and procedures is provided in the following appendices:

- Guidance for the specific timing of PK, immunogenicity, and pharmacodynamic sample collection: [Appendix 2](#) Schedule of Pharmacokinetic, Immunogenicity, and Pharmacodynamic Blood Sample Collection.
- Specific pharmacodynamic analyses to be conducted: [Appendix 3](#) List of Pharmacodynamic.
- Guidance for ECOG assessment: [Appendix 4](#) Eastern Cooperative Oncology Group Performance Status.
- Specific clinical laboratory tests to be conducted: [Appendix 5](#) Clinical Laboratory Tests.
- NYHA Classification: [Appendix 6](#) New York Heart Association Classification.

Footnotes for Schedule of Assessments (additional assessment and procedure details are provided in Protocol Section 8):

- Unless specified, procedure is to be completed within ± 72 hours of scheduled time point and performed prior to administration of study drug.
- Any clinical assessment, laboratory test, or additional non-specified test may be obtained at any time, if clinically indicated.
- A complete physical examination including height and weight will be performed at screening. A limited physical examination (e.g., symptom-directed examination of specific organ systems/body area) should be conducted at the specified time points after screening.

- d. Height is only required to be recorded at screening. Weight is required to be recorded pre-dose at Day 1 of each cycle. After Cycle 1, the FPA150 dose will be recalculated at each infusion visit only if the patient's weight has changed > 10% from Cycle 1, Day 1. Weight will also be recorded at the final EOT visit.

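### The 7-day limit on Grade 4 neutropenia in the DLT definition has no effect, because a separate bullet counts every Grade 4 laboratory value

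*Protocol*

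**What the plan says.** Protocol Section 4.1.2.2.1 defines a DLT as any one of a list of events, whatever the attribution, unless clearly due to the disease or an extraneous cause. Two of the bullets matter here.

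- The hematologic bullet includes "Grade 4 neutropenia lasting more than 7 days". It separately covers febrile neutropenia, infection with a low ANC, Grade 4 thrombocytopenia, and Grade 3 thrombocytopenia with bleeding.
- The laboratory bullet reads "Any Grade 4 laboratory value regardless of clinical sequelae". It has no duration condition and no exception for hematology.

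The synopsis repeats the laboratory bullet and has "Grade 4 neutropenia lasting for more than 7 days" in its hematologic bullet.

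Appendix 5, Table 15 lists ANC among the clinical laboratory tests. The synopsis section on the combination lead-in adopts the monotherapy criteria, and the immune-related exemptions added there and in Section 4.1.2.2.2 concern Grade 3 events only. Table 6 turns the DLT count into a dosing decision. SAP Section 7.1.7 summarises DLTs but does not define them.

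**The concern.** A duration limit on Grade 4 neutropenia makes sense only if shorter events are meant to be excluded. The laboratory bullet brings them back in. The list therefore contains a condition that does nothing, and its literal result contradicts the limit it states.

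DLT incidence is a primary Phase 1a endpoint (protocol Table 1). The monotherapy recommended dose is already set at 20 mg/kg (Section 4.1.2), so the rule's live use is the combination safety lead-in. There, a single patient can change the next step under Table 6.

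**Working it through.** **1. Do the two bullets ever disagree with the laboratory bullet alone?** Take Grade 4 neutropenia inside the 21-day window, without fever or infection and not clearly due to disease or an extraneous cause.

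| Duration | Hematologic bullet | Laboratory bullet | DLT as written |
|---|---|---|---|
| 3 days | no | yes | yes |
| 7 days | no | yes | yes |
| 8 days | yes | yes | yes |
| 12 days | yes | yes | yes |

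Without a Grade 4 value, neither of these two rules applies. In every case the combined result equals the laboratory bullet alone, so the 7-day condition never decides anything. The exception for disease or extraneous causes applies to the whole list and does not rescue it.

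**2. What does one such event do under Table 6?** It moves 0/3 to 1/3, which means three more patients and another 21-day window. If another patient also has a DLT, it moves 1/3 to 2/3 or 1/6 to 2/6. FPA150 then goes down one level, from 20 to 10 mg/kg, although the synopsis also allows intermediate doses.

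**3. How large could the effect be?** The plan states no figure to reproduce. Let q be the rate of uncomplicated Grade 4 neutropenia of 7 days or less, and a the rate of all other DLTs. Both are assumptions and are taken as independent. With brief events counted, the per-patient DLT probability is p = 1 − (1 − a)(1 − q). Table 6 clears a level at 0/3, or at 1/3 followed by 0/3:

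P(clear) = (1 − p)³ + 3p(1 − p)⁵

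For example, with a = 10% and q = 5%: p = 1 − 0.90 × 0.95 = 0.145, and P(clear) = 0.855³ + 3 × 0.145 × 0.855⁵ = 0.625 + 0.199 = 0.824. With q = 0 it is 0.906, so the loss is 8.2 points.

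| a | q = 0 | q = 1% | q = 2% | q = 5% | Loss at 1% | Loss at 5% |
|---|---|---|---|---|---|---|
| 0% | 100% | 99.9% | 99.5% | 97.3% | 0.1 | 2.7 |
| 5% | 97.3% | 96.3% | 95.2% | 91.0% | 1.0 | 6.3 |
| 10% | 90.6% | 89.1% | 87.5% | 82.4% | 1.5 | 8.2 |
| 20% | 70.9% | 69.1% | 67.4% | 62.2% | 1.7 | 8.7 |

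Losses are in percentage points, from unrounded values. The chance of at least one brief event in the first three patients is 1 − (1 − q)³: 3.0%, 5.9% and 14.3% for q = 1%, 2% and 5%.

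**4. Could a 7-day limit be applied from scheduled data?** In Appendix 1, Table 12, the row "Clinical Safety Laboratory Tests" has Cycle 1 entries on Days 1 and 8 only. Footnote n adds Day 15 for PK sampling. The next scheduled ANC after Day 8 is at Cycle 2 Day 1, study Day 22:

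- nominal gap: 22 − 8 = 14 days
- shortest with ±3-day windows: (22 − 3) − (8 + 3) = 8 days
- longest: (22 + 3) − (8 − 3) = 20 days

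The gap always exceeds 7 days. A Grade 4 value on Day 8 that has recovered by Cycle 2 cannot be placed above or below 7 days from the scheduled tests alone.

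**The case against.** The strongest reply is that the text, read literally, gives one answer and a cautious one. The defect is then an idle clause, and two readers diverge only if one of them lets the specific rule override the general. That is fair. The protocol states no such precedence, so the point is that the literal result defeats a limit the same list sets out. Overlap alone is harmless: Grade 4 thrombocytopenia is also covered twice, but with no duration condition to be defeated.

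The reply also notes that few cases would be affected, and this stands. Section 2.2.5.4 reports no DLTs in escalation up to 20 mg/kg, and neutropenia is not among the events named in Sections 2.2.5.5 and 2.2.5.6. Section 6.4.5 narrows things further: "Any dose modifications for pembrolizumab-related toxicity in patients enrolled on the Phase 1a Safety Lead-in will be considered a DLT" whatever the neutropenia rule says.

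Four stronger readings are tempting, and the documents do not support them.

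- **Table 10 shows that every Grade 4 event was meant to count.** Its discontinuation row reads "Grade 3 which does not recover to baseline or Grade 1 within 28 days Any Grade 4". But it governs an individual patient's dosing for FPA150-related toxicity, whereas DLTs are counted regardless of attribution. Section 4.1.2.4 expressly recognises discontinuations for toxicity that fall short of the DLT criteria. The evidence on intent is the Amendment 1 log, which records the 7-day wording being added and so suggests a deliberate limit. The log does not mention the laboratory bullet and cannot override current text.
- **Longer Grade 3 neutropenia would count while a 6-day Grade 4 event would not.** The bullet concerned is "Other Grade 3 laboratory values that are not of clinical significance according to Investigator and Sponsor agreement that do not resolve within 72 hours". It opens as a residual category and applies only to values agreed not to be clinically significant, so the paradox does not follow.
- **Repeat ANCs rest solely on discretion.** Appendix 1, footnote b does say "Any clinical assessment, laboratory test, or additional non-specified test may be obtained at any time, if clinically indicated". But Section 8.12.4 also requires unresolved AEs to be followed to resolution, and Sections 8.5 and 8.12.2 make a clinically significant laboratory abnormality an AE. What is missing is timing.
- **The monotherapy recommended dose is in doubt.** Nothing supports this. The literal rule can only add DLTs, and none was reported.

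**Conclusion.** The inconsistency is real and appears in both the synopsis and Section 4.1.2.2.1. As written, the 7-day limit is inoperative, and brief uncomplicated Grade 4 neutropenia is a DLT. No current text in the protocol or SAP repairs this.

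The expected consequence is small and leans toward caution: at most some over-counting in the lead-in. The 0.1 to 8.7 point range rests entirely on assumed rates and shows how sensitive the rule is, not what to expect. Correction is worthwhile because the definition feeds a primary endpoint, a dosing rule and the SAP's DLT summary, and because it costs little.

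**What to change.** In the synopsis and in Section 4.1.2.2.1, insert *other* so that the laboratory bullet covers any other Grade 4 value, and add: *(Grade 4 neutropenia is assessed only under the hematologic bullet)*. Febrile or infected cases, Grade 4 thrombocytopenia and all remaining Grade 4 laboratory values stay DLTs.

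Also state that ANC is repeated after any Grade 4 value at times that show whether it lasts more than 7 days. One repeat draw may not be enough: a value still at Grade 4 on day 4 leaves the question open. This gives timing to follow-up that Section 8.12.4 already requires.

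The cost is one edited bullet in two places, one sentence on timing, and a few blood draws in affected patients. Planned sample size and scheduled visits are unchanged, and Table 10 needs no edit.

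If the sponsor wants every Grade 4 neutropenia to count, delete the 7-day phrase in both places instead. No repeat-ANC rule is then needed for DLT classification.

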4.1.2.2.2 FPA150 Combined with Pembrolizumab (Safety Lead-in)

Additional DLT Considerations for the Combination of FPA150 and Pembrolizumab

Because pembrolizumab is a known immune checkpoint inhibitor and one of the proposed mechanisms of action of FPA150 is immune checkpoint blockade, immune-related adverse events (irAEs) are anticipated with this combination. An irAE is defined as a clinically significant AE that is associated with study drug exposure, of unknown etiology, and is consistent with an immune-mediated mechanism. Based on that background, the first occurrence of the following irAEs will not be considered a DLT because they are expected with immune therapy:

- Grade 3 tumor flare (defined as local pain, irritation, or rash localized at sites of known or suspected tumor)
- Grade 3 rash
- Grade 3 immune-related adverse event (irAE) that resolved to a Grade 1 or less within 14 days
- Transient (resolving within 6 hours of onset) Grade 3 infusion-related AE

A second occurrence of these events (except Grade 3 tumor flare) either in the same or different patient during the DLT period will be considered a DLT

4.1.2.3 Dose-Limiting Toxicity Evaluation and Dose Escalation (FPA150 Monotherapy and Combination Safety Lead-in)

The DLT evaluation interval begins on the first day of treatment upon start of infusion and continues for 21 days. In Phase 1a Dose Escalation, patients' second dose must be at least 21 days after the first dose.

Review of safety, PK and pharmacodynamic profiles may inform decisions to add cohorts with alternative dose levels or dose regimens (eg, different dosing frequency, higher dose levels) in order to reach an optimal target exposure.

All dose escalation decisions will be based on the assessment of DLTs and overall safety and tolerability, and will be made after the last patient enrolled in each cohort has completed the first treatment cycle (ie, 21 days). Dose escalation decisions will be agreed upon by the CRC as outlined in Section [4.1.1](#).

Patients who receive at least one dose of study drug during the 21-day evaluation interval, or patients who discontinue study treatment for drug-related AEs before the DLT evaluation interval is complete, will be considered evaluable for DLT determination. Patients who discontinue study treatment for reasons other than drug-related AEs before the DLT evaluation interval is complete may be replaced. In consultation with Investigators, the Sponsor may open cohorts at dose levels between the dose levels proposed in the protocol.

For monotherapy dose escalation an accelerated titration design enrolling at least 1 patient at each dose level is planned for dose levels 0.01, 0.03, 0.1, and 0.3 mg/kg. Dose escalation to the next dose level may proceed after at least 1 patient completes the 21-day evaluation interval. If a single patient experiences a DLT or at least 2 patients experience moderate AEs (at any dose level) during the 21-day evaluation interval, additional patients will be enrolled at the current dose level and standard 3+3 dose escalation criteria will apply for that cohort as well as all subsequent dosing cohorts. Moderate AEs are defined as \geq Grade 2 AEs regardless of attribution (except for those events clearly due to the underlying disease or extraneous causes). Grade 2 laboratory values will not be considered as moderate AEs for this purpose unless accompanied by clinical sequelae.

The algorithm outlined in Table 5 will be used for all standard 3+3 dose escalation decisions in Phase 1a monotherapy. If not already applied at a lower dose level for the reasons stated above, escalation for dose levels \geq 1 mg/kg will follow standard 3+3 dose escalation criteria.

Table 5: Phase 1a Algorithm for FPA150 Monotherapy Dose-Escalation Decisions

Number of Patients with DLT at a Given Dose Level	Dose Escalation Decision Rule
0/3	Enroll 3 patients at next dose level (next/higher cohort)
1/3	Enroll 3 additional patients at current dose level (current cohort)
$\geq 2/3$	Stop enrollment. Enter 3 more patients at the previous dose level (previous/lower cohort), if only 3 were previously entered, or at an intermediate dose level
1/6	Enroll 3 patients at next dose level (next/higher cohort)
$\geq 2/6$	Stop enrollment. Enter 3 more patients at the lower dose level (previous/lower cohort), if only 3 were previously entered, or at an intermediate dose level

Abbreviations: DLT = dose-limiting toxicity.

The algorithm outlined in [Table 6](#) will apply for dosing decisions for the FPA150 and pembrolizumab combination.

Table 6: Algorithm for Dose De-Escalation Decisions for FPA150 Safety Lead-In in Combination with Pembrolizumab in Phase 1a

Number of Patients with DLT at a Given Dose Level	Dosing Decision Rule
0/3	Proceed with enrolment of up to 10 total patients at that dose level for additional safety assessment
1/3	Enrol 3 additional patients at current dose level (current cohort)
$\geq 2/3$	Stop enrolment at current cohort and de-escalate FPA150 to one dose level below current dose
1/6	Proceed with enrolment of up to 10 total patients at that dose level
$\geq 2/6$	Stop enrolment at current cohort and de-escalate FPA150 to one dose level below current dose.

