7.3 Patient Replacement

Patients in Phase 1a Dose Escalation or Phase 1a Combination Safety lead-in will be replaced if they are unevaluable for DLT (refer to Section 4.1.2.2). Patients in Phase 1a Dose Exploration or Phase 1b Dose Expansion will not be replaced.

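### The rules for who counts towards Tables 5 and 6 contradict each other, and none says whether a replaced patient's DLT stays in the count

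*Protocol*

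**What the plan says.** **DLT definition (Protocol 4.1.2.2.1).** "DLTs during Phase 1a Dose Escalation are defined as any of the following events regardless of attribution", with one carve-out: "except for those events clearly due to the underlying disease or extraneous causes". Section 4.1.2.2.2 adds exceptions for the combination but does not bring relatedness back as a general test.

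**Window (4.1.2.3).** "The DLT evaluation interval begins on the first day of treatment upon start of infusion and continues for 21 days".

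**Evaluability (synopsis and 4.1.2.3).** Two groups are evaluable. The first is "Patients who receive at least one dose of study drug during the 21-day evaluation interval". The second is "patients who discontinue study treatment for drug-related AEs before the DLT evaluation interval is complete, will be considered evaluable for DLT determination".

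**Replacement.** Section 4.1.2.3 is permissive and depends on relatedness: "Patients who discontinue study treatment for reasons other than drug-related AEs before the DLT evaluation interval is complete may be replaced". Section 7.3 is mandatory and depends on evaluability. It says that escalation and Safety Lead-in patients "will be replaced if they are unevaluable for DLT (refer to Section 4.1.2.2", and the section it cites is the DLT definition. Section 6.4.5 says that in the Safety Lead-in a dose modification for pembrolizumab-related toxicity is a DLT and that the patient has to be replaced.

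**Analysis set (Protocol 9.2 and SAP 3.1.3).** A patient is included with at least two FPA150 doses and a completed Cycle 1, or with a DLT in Cycle 1. SAP 7.1.7 reports DLTs on this set.

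**The concern.** Tables 5 and 6 act on counts such as 0/3, 1/3 and 1/6. With three or six patients, one patient wrongly included, or one DLT wrongly left out, changes the decision. There are three separate weaknesses.

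- The one-dose rule sets no minimum observation. A patient who leaves in the first days without an event can fill a place in 0/3.
- Evaluability, replacement and the analysis set are defined differently. The denominator used for a dosing decision need not be the one in the DLT table of the study report.
- A patient can have a DLT and also be replaceable, and the documents do not say what then happens to the DLT. Amendment 1 changed the DLT definition so that it applies regardless of attribution, but the replacement sentence in 4.1.2.3 still asks for a relatedness judgement. In an open-label combination where immune-related events are expected, that judgement is hard to make.

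In the Safety Lead-in, 0/3 or 1/6 opens enrolment of up to 10 patients at that dose. Cohort 1bC1, with up to 30 patients, follows once the combination dose is set.

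**Working it through.** **Step 1. Four patients, each taken through every rule.**

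| Patient | 4.1.2.3 evaluable? | 4.1.2.3 replacement | 7.3 replacement | 9.2 / SAP 3.1.3 |
|---|---|---|---|---|
| A: one dose, leaves on Day 3 for progression, no event | Yes, no DLT | Allowed | No (not unevaluable) | Excluded |
| B: qualifying Grade 3 event, judged not drug-related but not clearly due to disease; stops in the window | Yes, DLT | Allowed | No | Included as DLT |
| C: Lead-in patient, pembrolizumab modified in Cycle 1 for related toxicity | Yes, DLT under 6.4.5 | Not covered, but required by 6.4.5 | No | Included as DLT |
| D: 21 days observed, no DLT, no second dose | Yes, no DLT | Not covered | No | Excluded |

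Every row contains a disagreement. The drug-related limb of the evaluability rule adds nobody, because those patients have already had one dose. Relatedness therefore affects replacement only. Patient D arises because 4.1.2.3 puts the second dose in dose escalation at least 21 days after the first, so a patient can finish the window and still lack the two doses that 9.2 asks for.

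**Step 2. Size.** The documents state no operating characteristic for the 3+3 or de-escalation rule, so there is no planned figure to reproduce. The true DLT rates and the shares below are all assumed.

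A dose clears on 0/3, or on 1/3 followed by 0/3:

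P(clear) = (1−p)³ + 3p(1−p)⁵

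At p = 1/3: 0.296 + 0.132 = 0.428.

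*If a share f of DLT patients were replaced and their DLTs dropped*, the effective rate is p′ = p(1−f)/(1−pf). For p = 1/3:

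| f | p′ | P(clear) |
|---|---|---|
| 0 | 0.333 | 0.428 |
| 0.20 | 0.286 | 0.524 |
| 0.30 | 0.259 | 0.580 |
| 0.50 | 0.200 | 0.709 |

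Other assumed rates move the same way. At p = 0.20, P(clear) goes from 0.709 to between 0.744 (f = 0.10) and 0.887 (f = 0.50). At p = 0.30 it goes from 0.494 to between 0.539 and 0.759.

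*If one of three is an unobserved early leaver who is kept as DLT-free*, only two patients can show a DLT. At p = 0.40, P(0/3) = 0.6² = 0.36 instead of 0.6³ = 0.216. This is conditional on such a patient being present and retained.

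**The case against.** A reader might infer that the plan removes DLTs from the count whenever the investigator calls them unrelated. The documents do not say that. Replacing a patient does not delete the patient's DLT. Tables 5 and 6 count patients with a DLT, 9.2 and SAP 3.1.3 keep everyone with a DLT in Cycle 1, and 6.4.5 treats having a DLT and being replaced as compatible. What stands is the silence: no text ties the replaced patient's DLT to the decision count.

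A reader might also infer that every early leaver is bound to count as DLT-free. That goes too far, because 4.1.2.3 allows the same patient to be replaced and 9.2 excludes the patient from the reported set. Both effects would need discretion to go the unsafe way: the DLT patient replaced and dropped, the early leaver kept.

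Three further points are fair.

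- Section 4.1.2 records the monotherapy recommended dose as set by 28 January 2019, and 2.2.5.4 reports no DLTs up to 20 mg/kg. Table 5 has largely served its purpose.
- Decisions also rest on overall safety, on cumulative review by the Cohort Review Committee, and on discontinuations outside the DLT criteria.
- The 7.3 cross-reference looks like a renumbering slip. The Amendment 1 log gives 4.1.2.2 as the evaluation section.

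These points reduce the exposure but do not settle the contradiction. Section 4.1.2.3 makes decisions wait until the last patient enrolled has completed Cycle 1, but it does not require each counted patient to have been observed for 21 days.

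**Conclusion.** The point holds as an inconsistency with a possible effect on dose decisions. It is not a demonstrated bias. The one-dose rule permits an unobserved patient in the denominator. Sections 4.1.2.3, 6.4.5, 7.3 and 9.2 with SAP 3.1.3 cannot all be applied together. The fate of a replaced patient's DLT is unstated.

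If the gaps were resolved in the permissive direction, each would make a dose easier to clear. The figures (0.43 to between 0.52 and 0.71 at a DLT rate of 1/3; 0.36 against 0.22 at 40%) show direction and order of size only. They rest on assumed DLT rates and shares and, for the first pair, on the DLTs actually being dropped. The main live exposure is the combination Safety Lead-in, together with the denominator of the final DLT table.

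**What to change.** Write one evaluability and replacement definition, and use it in the synopsis, 4.1.2.3, 6.4.5, 7.3, 9.2 and SAP 3.1.3, both for the Table 5 and 6 decisions and for the DLT analysis set. It should state that:

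1. any DLT under 4.1.2.2 within the window stays in the count, whatever the relatedness assessment and whether or not the patient is replaced;
2. a patient without a DLT enters the denominator only after the full 21-day observation, and is otherwise replaced.

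The two-dose condition in 9.2 and SAP 3.1.3 has to be reconciled with item 2, and the replacement sentence in 6.4.5 with item 1. Correct the cross-reference in 7.3 so that it points to the evaluability text in 4.1.2.3.

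The cost is wording in the protocol and SAP, plus an occasional replacement patient, which 7.3 already foresees.
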